8.1.3.1 Memorial Anxiety Scale for Prostate Cancer (MAX-PC)

Per the MAX-PC ([Appendix 3](#)), there are 18 questions designed to better understand how subjects cope with aspects of their treatment for prostate cancer and the medical tests frequently involved in their care. Responses to the items have 4 possible integer scores ranging from 0 (Not at all) to 3 (Often), so that higher scores reflect worse symptoms. The total MAX-PC score is the sum of the scores from the 18 items and ranges from 0 to 54. The total score is missing if any of the individual scores are missing.

The 18 items are categorized into subscales of Prostate Cancer Anxiety (items 1-11), PSA Anxiety (items 12-14), and Fear of Recurrence (items 15-18). The score for each subscale is the sum of the scores from the items within each subscale so that subscale scores range from 0 to 33, from 0 to 9, and from 0 to 12, respectively. The score for each subscale is missing if any of the individual scores in the subscale is missing.

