APPENDIX 3: MEMORIAL ANXIETY SCALE FOR PROSTATE CANCER (MAX-PC)

The Modified 18-Item Memorial Anxiety Scale for Prostate Cancer

YOUR FEELINGS ABOUT PROSTATE CANCER AND PROSTATE SPECIFIC ANTIGEN TESTS

We would like to better understand how patients cope with aspects of their treatment for prostate cancer and the medical tests frequently involved in their care.

I. Below is a list of comments made by men about prostate cancer. Please indicate by circling the number next to each item how frequently these comments were true for you *during the past week*; not at all, rarely, sometimes, often.

	Not at all	Rarely	Sometimes	Often
1. Any reference to prostate cancer brought up strong feelings in me.	0	1	2	3
2. Even though it's a good idea, I found that getting a PSA test scared me.	0	1	2	3
3. Whenever I heard about a friend or public figure with prostate cancer, I got more anxious about my having prostate cancer.	0	1	2	3
4. When I thought about having a PSA test, I got more anxious about my having prostate cancer.	0	1	2	3
5. Other things kept making me think about prostate cancer.	0	1	2	3
6. I felt kind of numb when I thought about prostate cancer.	0	1	2	3
7. I thought about prostate cancer even though I didn't mean to.	0	1	2	3
8. I had a lot of feelings about prostate cancer, but I didn't want to deal with them.	0	1	2	3
9. I had more trouble falling asleep because I couldn't get thoughts of prostate cancer out of my mind.	0	1	2	3
10. I was afraid that the results from my PSA test would show that my disease was getting worse.	0	1	2	3
11. Just hearing the words "prostate cancer" scared me.	0	1	2	3

II. For the next three questions, please indicate how frequently these situations have *EVER* been true for you.

	Not at all	Rarely	Sometimes	Often
12. I have been so anxious about my PSA test that I have thought about delaying it.	0	1	2	3
13. I have been so worried about my PSA test result that I have thought about asking my doctor to repeat it.	0	1	2	3
14. I have been so concerned about my PSA test result that I have thought about having the test repeated at another lab to make sure they were accurate.	0	1	2	3

III. Listed below are a number of statements concerning a person's beliefs about their own health. In thinking about the *past week*, please indicate how much you agree or disagree with each statement: strongly agree, agree, disagree, or strongly disagree. Please circle the number of your answer.

	Strongly agree	Agree	Disagree	Strongly disagree

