15. Because cancer is unpredictable, I feel I cannot plan for the future.	0	1	2	3
16. My fear of having my cancer getting worse gets in the way of my enjoying life.	0	1	2	3
17. I am afraid of my cancer getting worse.	0	1	2	3
18. I am more nervous since I was diagnosed with prostate cancer	0	1	2	3

PSA: prostate specific antigen.

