8.1.3 Patient Reported Outcomes (PROs)

The following PROs are reported at baseline and at every 12-month visit. For each of the scores defined below, the change from baseline at each timepoint and maximum change (toward favorable outcome) during any assessment within 36-month after randomization, including unscheduled visit, minus the baseline score.

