12.6.2.2 PROs

For each PRO total score and pooled domain score or sub-score defined in [Section 8.1.3](#), actual values at baseline and change from baseline at 12, 24, and 36 months visits post randomization will be summarized in the ITT and PP analysis sets in each treatment arm. The best change within 36 months post-baseline will be summarized and compared between the arms. The responses to individual question items will not be summarized except for the EPIC-CP overall urinary function question, which will be presented at baseline and its shift change presented at post-randomization.

To assess potential missing individual items in each PRO questionnaire, a sensitivity analysis in the ITT analysis set will be conducted to calculate total scores and pooled domain scores by summing up all available individual items regardless of any missing individual score.

PRO results will be provided in a listing.

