Appendix 3 Memorial Anxiety Scale for Prostate Cancer (MAX-PC)

The Modified 18-Item Memorial Anxiety Scale for Prostate Cancer

YOUR FEELINGS ABOUT PROSTATE CANCER AND PROSTATE SPECIFIC ANTIGEN TESTS

We would like to better understand how patients cope with aspects of their treatment for prostate cancer and the medical tests frequently involved in their care.

I. Below is a list of comments made by men about prostate cancer. Please indicate by circling the number next to each item how frequently these comments were true for you *during the past week*; not at all, rarely, sometimes, often.

	Not at all	Rarely	Sometimes	Often
1. Any reference to prostate cancer brought up strong feelings in me.	0	1	2	3
2. Even though it's a good idea, I found that getting a PSA test scared me.	0	1	2	3
3. Whenever I heard about a friend or public figure with prostate cancer, I got more anxious about my having prostate cancer.	0	1	2	3
4. When I thought about having a PSA test, I got more anxious about my having prostate cancer.	0	1	2	3
5. Other things kept making me think about prostate cancer.	0	1	2	3
6. I felt kind of numb when I thought about prostate cancer.	0	1	2	3
7. I thought about prostate cancer even though I didn't mean to.	0	1	2	3
8. I had a lot of feelings about prostate cancer, but I didn't want to deal with them.	0	1	2	3
9. I had more trouble falling asleep because I couldn't get thoughts of prostate cancer out of my mind.	0	1	2	3
10. I was afraid that the results from my PSA test would show that my disease was getting worse.	0	1	2	3
11. Just hearing the words "prostate cancer" scared me.	0	1	2	3

II. For the next three questions, please indicate how frequently these situations have *EVER* been true for you.

	Not at all	Rarely	Sometimes	Often
12. I have been so anxious about my PSA test that I have thought about delaying it.	0	1	2	3
13. I have been so worried about my PSA test result that I have thought about asking my doctor to repeat it.	0	1	2	3
14. I have been so concerned about my PSA test result that I have thought about having the test repeated at another lab to make sure they were accurate.	0	1	2	3

III. Listed below are a number of statements concerning a person's beliefs about their own health. In thinking about the *past week*, please indicate how much you agree or disagree with each statement: strongly agree, agree, disagree, or strongly disagree. Please circle the number of your answer.

	Strongly agree	Agree	Disagree	Strongly disagree

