15. Because cancer is unpredictable, I feel I cannot plan for the future.	0	1	2	3
16. My fear of having my cancer getting worse gets in the way of my enjoying life.	0	1	2	3
17. I am afraid of my cancer getting worse.	0	1	2	3
18. I am more nervous since I was diagnosed with prostate cancer	0	1	2	3

PSA: prostate specific antigen.

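### The SAP's MAX-PC scoring rule contradicts its own form for items 15–18; summing the printed codes would reverse the Fear of Recurrence subscale

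*SAP*

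**What the plan says.** SAP 8.1.3.1 refers to the form in SAP Appendix 3 and gives a single response scale for the whole instrument, "ranging from 0 (Not at all) to 3 (Often), so that higher scores reflect worse symptoms". The total is the plain sum of the 18 items (0 to 54). The subscales are plain sums of items 1–11 (Prostate Cancer Anxiety), 12–14 (PSA Anxiety) and 15–18 (Fear of Recurrence), "so that subscale scores range from 0 to 33, from 0 to 9, and from 0 to 12, respectively". No recoding step is given.

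The form does not use one scale throughout. Parts I and II (items 1–14) run from *Not at all* = 0 to *Often* = 3. Part III (items 15–18) asks for agreement: "strongly agree, agree, disagree, or strongly disagree. Please circle the number of your answer". Its columns are printed *Strongly agree* = 0, *Agree* = 1, *Disagree* = 2, *Strongly disagree* = 3. Item 17, for example, reads "I am afraid of my cancer getting worse". Protocol Appendix 3 prints the same form in the same order, including item 16, "My fear of having my cancer getting worse gets in the way of my enjoying life".

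SAP 8.1.3 then defines, for every PRO score, a "maximum change (toward favorable outcome) during any assessment within 36-month after randomization". SAP 12.6.2.2 says: "The best change within 36 months post-baseline will be summarized and compared between the arms".

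**The concern.** All four Part III items are worded so that agreement means more fear or anxiety, yet agreement carries the low codes. The scale described in SAP 8.1.3.1 is therefore wrong for 4 of 18 items, and its stated direction conflicts with the form it cites. If the printed codes are summed as the text describes, Fear of Recurrence runs backwards, and the total adds 14 items in one direction and 4 in the other.

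Differences in quality of life between arms are a secondary objective (SAP 5.2), and SAP 7.2.1 names the Fear of Recurrence subscore. A man whose fear falls would be reported as worse.

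Nothing else in the SAP would catch this. SF-12 scoring is assigned to named software (SAP 8.1.3.2), but MAX-PC has no named software, and SAP 14.0 lists no scoring reference for it. The stated score ranges hold under either coding. Individual item responses will not be tabulated, apart from one EPIC-CP question (SAP 12.6.2.2).

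**Working it through.** **Inputs.** Item grouping, sum rule and ranges: SAP 8.1.3.1. Printed codes and item wording: SAP Appendix 3 and Protocol Appendix 3. Best-change definition and its use: SAP 8.1.3 and 12.6.2.2. Everything below except step 1 applies only if the printed codes are summed.

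**1. The plan's own ranges.** Number of items × 3: 11 × 3 = 33, 3 × 3 = 9, 4 × 3 = 12, and 33 + 9 + 12 = 18 × 3 = 54. All reproduce. They depend only on the 0–3 span of each item, not on its direction, so a range check cannot reveal a reversal.

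**2. Text against form.**

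| Items | Scale in SAP 8.1.3.1 | Scale on the form | Most distressed answer |
|---|---|---|---|
| 1–14 | *Not at all* 0 to *Often* 3 | the same | 3 |
| 15–18 | *Not at all* 0 to *Often* 3 | *Strongly agree* 0 to *Strongly disagree* 3 | 0 |

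**3. Fear of Recurrence.** With printed code x on each item, the score in the intended direction is the sum of (3 − x) = 12 − (sum of x). Enumerating all 4⁴ = 256 answer patterns confirms this in every case. The most fearful man scores 0 instead of 12, and every change score has the wrong sign.

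**4. Total.** Least anxious on every item: 14 × 0 + 4 × 3 = 12, instead of 0. Most anxious on every item: 14 × 3 + 4 × 0 = 42, instead of 54. A one-category improvement on all 18 items reads −14 + 4 = −10, instead of −18.

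More generally, for a shift of a per item on items 1–14 and b per item on items 15–18, the correct total change is 14a + 4b and the printed one is 14a − 4b:

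| Fear shift relative to the other items | Share of the effect kept in the total |
|---|---|
| b = 0 | 14/14 = 100% |
| b = a | 10/18 = 56% |
| b = 2a | 6/22 = 27% |
| b = 3.5a | 0% |
| b = 5a | −6/34 = −18% |
| a = 0 (fear only) | −100% |

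The documents do not say where a treatment effect would fall, so these ratios are illustrations.

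**5. Best change.** With lower taken as favorable, best change is the most negative change from baseline. On printed codes each change is minus the intended change, so the selected value is −(largest intended change), which comes from the most fearful follow-up visit. This was checked for all 13⁴ = 28,561 combinations of a baseline and three visit scores.

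- Intended 8, then 6, 4, 5: best change −4 (improved). Printed 4, then 6, 8, 7: best change +2 (worse).
- Intended 6, then 4, 3, 8: best change −3, at month 24. Printed 6, then 8, 9, 4: best change −2, at month 36, when fear had risen by 2.

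In the second example, flipping the sign of the reported −2 gives +2, not −3. Best change must be re-derived from the visit scores.

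**6. A minor related point.** One sensitivity analysis in SAP 12.6.2.2 sums whatever items were answered. A skipped item then counts as 0, which means no symptom on EPIC-CP, I-PSS and MAX-PC items 1–14. I-PSS with six of seven items at 3 gives 18, against 18/6 × 7 = 21 prorated (moderate against severe on the form's bands). An EPIC-CP domain with two of three items at 3 gives 6, against 6/2 × 3 = 9.

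**The case against.** The reversal of actual data is not shown. SAP 8.1.3.1 states the right direction, and a programmer who takes that statement seriously would have to recode items 15–18. The CRF and the table shells cited in SAP Appendix 2 are not available, and either could already hold the correct coding. This stands, and it is why the consequence is stated conditionally. It does not remove the contradiction: the described response scale is wrong for four items whatever the CRF stores, and the recode appears nowhere in either document.

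The scope is also limited: one of three MAX-PC subscales and 12 of 54 points of the total, in one of four instruments. The SAP names no specific PRO test, and SAP 12.6.1.2 rests study success on the primary endpoint alone. Item-level data would allow exact rescoring. All of this is fair and bounds the severity, but a named secondary subscore could still be reported with the wrong sign.

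The effect shares in step 4 rest on assumed ratios. The total changes sign only if fear items shift more than 3.5 times as much per item as the others, and nothing in the documents suggests that they would. The identity in step 3 and the best-change result in step 5 need no such assumption.

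The missing-item point concerns a single sensitivity analysis; the main rule for MAX-PC, EPIC-CP and I-PSS sets an incomplete score to missing. The I-PSS severity bands appear only on the form and are not an analysis category. Proration is a choice. The main point does not depend on it.

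**Conclusion.** The concern holds. SAP 8.1.3.1 misdescribes the response scale of MAX-PC items 15–18 and gives a scoring rule that, applied to the printed codes, contradicts its own statement that higher is worse. On those codes Fear of Recurrence is exactly reversed, the total is partly distorted, and best change is drawn from the wrong visit.

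The mismatch between text and form is certain. Its effect on the stored data is not, because it depends on how the CRF of 26JUN2019 holds these four items. The point should be corrected before the PRO scores are derived.

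**What to change.** 1. Check how the CRF of 26JUN2019 stores items 15–18, so that a recode is neither omitted nor applied twice.
2. In SAP 8.1.3.1, give the agreement scale for items 15–18. State either that they are recoded as 3 minus the printed code before the Fear of Recurrence subscale and the total are computed, or that they are already stored with *Strongly agree* = 3 and no recode is applied.
3. In SAP 8.1.3, state that a decrease is favorable for MAX-PC and that best change is derived after any recode. The direction already follows from higher being worse; the order of operations does not.
4. Minor, SAP 12.6.2.2: replace the sum of answered items with a prorated score (mean of answered items × number of items) when at least half are answered, otherwise missing. That means 6 of 11, 2 of 3 and 2 of 4 items for the MAX-PC subscales, 2 of 3 for each EPIC-CP domain and 4 of 7 for the I-PSS total, after any MAX-PC recode. MAX-PC and EPIC-CP totals are then sums of their subscales or domains. Proration assumes that skipped items resemble the answered ones, and the half-items threshold is a choice the SAP must fix.

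The cost is one check of the CRF coding, revised SAP wording and a few lines of programming. No new data are needed.

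### MAX-PC PSA Anxiety is rated over a lifetime, so the SAP's best-favourable-change comparison cannot show existing PSA anxiety resolving

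*SAP*

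**What the plan says.** **The form.** SAP Appendix 3 prints MAX-PC in three parts. Part I (items 1-11) asks about the past week. Part III (items 15-18) does too: "In thinking about the *past week*, please indicate how much you agree or disagree with each statement". Part II (items 12-14) does not: "For the next three questions, please indicate how frequently these situations have *EVER* been true for you". Its first item reads "I have been so anxious about my PSA test that I have thought about delaying it". Protocol Appendix 3 carries the same wording.

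**The scoring.** SAP 8.1.3.1 makes PSA Anxiety exactly the Part II block: "The 18 items are categorized into subscales of Prostate Cancer Anxiety (items 1-11), PSA Anxiety (items 12-14), and Fear of Recurrence (items 15-18". It gives the ranges as "subscale scores range from 0 to 33, from 0 to 9, and from 0 to 12, respectively". All 18 items are summed to a total of 0 to 54. Higher is worse, so a favourable change is a fall.

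**The analysis.** SAP 7.2.1 lists change from baseline in the MAX-PC total and in PSA Anxiety among the secondary efficacy endpoints. For every score, SAP 8.1.3 defines the change at each time point and the "maximum change (toward favorable outcome) during any assessment within 36-month after randomization". SAP 12.6.2.2 covers totals and sub-scores alike and compares the best change between arms, without naming a test. Nothing exempts PSA Anxiety or mentions its different recall period.

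**The concern.** A lifetime rating given at baseline already contains everything that happened before baseline. Later experience can add to it but can hardly take anything away. If a man once thought often about delaying a PSA test, that stays true at 12, 24 and 36 months, however calm he has become.

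The SAP nonetheless applies a measure of improvement to this subscale. Two misreadings are at stake. Similar results in the two arms could be taken as evidence that treatment does not relieve PSA anxiety, when the score could hardly have shown relief. An apparent improvement could be taken as benefit, when most of it would be error in recalling or repeating a lifetime answer. The same three items also sit in the MAX-PC total.

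**Working it through.** **1. Ranges and share of the total.** Inputs: item counts and 0-3 scoring from SAP 8.1.3.1.
- 11 × 3 = 33, 3 × 3 = 9, 4 × 3 = 12 and 18 × 3 = 54. The SAP's ranges reproduce.
- Lifetime share of PSA Anxiety: 3 of 3 items.
- Lifetime share of the total: 9/54 = 16.7%. Past-week points: 54 − 9 = 45.

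**2. What best change can be on the cumulative reading.** Take one 0-3 item at baseline, 12, 24 and 36 months, and suppose that it can only stay or rise. Best change = lowest post-baseline value − baseline value.
- Non-decreasing paths: C(7,4) = 35.
- Paths with a favourable best change: 0 of 35.
- On every path the lowest post-baseline value is the 12-month value, so best change equals the 12-month change.
- Paths with equal baseline and 12-month values: C(6,3) = 20. Best change is 0 on these and a worsening on the other 35 − 20 = 15.
- Four paths are flat throughout, so 35 − 4 = 31 rise at some point. Of these, 31 − 15 = 16 rise only after month 12, and best change records them as 0.

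These are counts of possible patterns, not probabilities. They show that best change is 0 or a worsening, and that it ignores new anxiety first reported after month 12.

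**3. The alternative reading of frequency.** A man might rate frequency as a share of all his PSA tests. Protocol 5.1 schedules PSA every 6 months for at least 36 months, so 36/6 = 6 further tests. As an illustration, anxiety at 2 of 3 tests before baseline (67%), then none at the next 6, gives 2/9 = 22%. He could truthfully move from *Often* to *Sometimes*. He could not truthfully return to *Not at all*.

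**4. How much improvement error alone can produce.** Suppose no true change, independent normal error, and error variance of (1 − reliability) in units of the score's variance. The documents give no reliability, so 0.5 to 0.9 is an assumed range. The expected lowest of three standard normal values is −3/(2√π) = −0.846, so mean best change = −0.846 × √(1 − reliability).

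| Assumed reliability | Formula (SD) | Simulation (SD) |
|---|---|---|
| 0.5 | −0.598 | −0.599 |
| 0.7 | −0.464 | −0.464 |
| 0.8 | −0.378 | −0.378 |
| 0.9 | −0.268 | −0.267 |

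Baseline is the lowest of four exchangeable readings in 1 case of 4, so about 75% of men would show some improvement. This treats the score as continuous. On a 0-9 integer score, ties and men already at 0 would reduce both figures. The artefact is expected in both arms, so it describes false improvement within an arm, not a difference between arms.

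**The case against.** Much of the case on the other side stands, and it limits the point.

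- **The subscale can still separate the arms.** If treatment prevented new PSA anxiety, control scores would rise more. That could appear in the 12-, 24- and 36-month changes, and in best change through the 12-month value. A reader might infer that favourable change is exactly 0 in both arms, or that the subscale can show nothing. Neither follows: best change can be a worsening, and only the resolution of existing anxiety is hidden.
- **A truthful fall is possible.** A reader might infer that every improvement is error. The items ask how frequently, and step 3 shows a reading under which a fall is honest. The documents do not show how men answer these items on repeat.
- **Current PSA fear is measured elsewhere.** Items 2, 4 and 10 ask about it over the past week and belong to Prostate Cancer Anxiety, which is reported separately. That subscale and Fear of Recurrence together make up the 0-45 score (33 + 12), so the new score adds little beyond them.
- **The structural effect is the same in both randomised arms.** A reader might infer a bias toward sipuleucel-T. The documents do not establish one. The trial is open-label. Men who start prostate cancer treatment also move to the Follow-up Phase (Protocol 6.8), where questionnaires come every 6 months (Protocol 8.7). Recall error or the number of readings could therefore differ by arm, but neither the direction nor the size can be derived.
- **The consequence is limited.** This is one subscale of one of four secondary instruments. Study success rests on a single primary test (SAP 12.6.1.2).

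The objection does not rescue the best-favourable-change comparison for PSA Anxiety. Even if the printed form is the instrument's usual form, the problem lies in the use the SAP makes of it.

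**Conclusion.** The point holds for the best-favourable-change comparison of PSA Anxiety. All three items carry a lifetime frame. On the ordinary cumulative reading the score cannot return to *Not at all* and can hardly fall, so the comparison cannot show existing PSA anxiety resolving, and most apparent improvement would be recall or response error. New anxiety can still register as a rise, although best change misses a rise that begins after month 12.

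The reach is the whole subscale (0-9) and 9 of the 54 points of the total (17%). A reader might infer that the total is invalid. It is not: 15 of 18 items, 45 of 54 points, concern the past week, so it is diluted rather than disabled. The primary endpoint is unaffected.

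The conclusion rests on the printed wording and on the cumulative reading of a lifetime question. The error sizes in step 4 also rest on assumed reliabilities and a continuous score, and the conclusion does not depend on them.

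**What to change.** 1. In SAP 8.1.3 and 12.6.2.2, exclude PSA Anxiety from the best-favourable-change comparison.
2. In its place, report by arm the proportion of men with any increase over baseline in PSA Anxiety, and state which visits count. Say alongside it that this is also subject to recall error and that men at the maximum at baseline cannot increase.
3. Keep the 18-item total as planned. Add, as a sensitivity analysis, change from baseline in the sum of the past-week items (1-11 and 15-18, range 0-45).
4. Before computing that sum, reconcile the direction of items 15-18. The form prints *Strongly agree* as 0 and *Strongly disagree* as 3, so a higher score there means less distress. SAP 8.1.3.1 treats higher as worse and states no reverse scoring. This also affects the planned total and Fear of Recurrence.

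Cost: SAP wording, one proportion and one derived score, all from data already collected. The downside is that the documents do not show the 15-item score to be validated, so it should be supportive only.
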